**NCT number : NCT03864900**

**Document date:2017.4.20**

## Study Protocol

**BACKGROUND:** Inconsistent anticoagulation therapy in AF patients is associated with a higher risk of stroke and abnormal bleeding. However, control of oral anticoagulation therapy in AF patients has been frequently reported as inadequate. Few theoretical based interventions have been tested for enhancing medication adherence in this population. Previous studies showed that the health belief model may offer some advantage over other behavior change theories for enhancing medication adherence in adult with chronic conditions.

**PURPOSE:** The purpose of the study is to investigate the efficacy of a health belief model based self-management of oral anticoagulant therapy intervention on the outcome of medication adherence and the mediators of knowledge, professional support, health belief, and self-efficacy in patients treated with oral anticoagulants for atrial fibrillation.

**METHODS:** The study is a randomized clinical trial with repeated measurements. A convenient sample of 72 adults who were treated with anticoagulants for atrial fibrillation was recruited from two teaching hospitals in northern Taiwan. Participants were randomly assigned 1:1 to either the control group (n = 36) or the intervention group (n = 36) after completion of baseline questionnaires. Allocation was balanced by site by using a minimization method. The health belief model based self-management intervention comprised two main components: a 60-minute individual face-to-face instruction and six follow-up telephone calls. Participants in the control group received regular medication education, 10-minute individual instruction for health knowledge and six follow-up telephone calls for concerning health. Data were collected at baseline, third month, and sixth month in both groups, by using self-administered questionnaires. The investigator administered the study questionnaire after obtaining informed consent from each subject. The data collection took place at the waiting areas outside the outpatient clinics during the patients' visits to the clinics. For subjects who were unable to read the questionnaire due to vision or other problems, the investigator read each question to help them complete the questionnaire. The instruments include the Atrial Fibrillation Knowledge Scale, Satisfaction Scale about Service and Warfarin Treatment, Belief about Anticoagulation Survey, and Self-Efficacy for Appropriate Medication Use Scale.

**DATA ANALYSIS:** Data were analyzed using the Statistical Package for Social Sciences 20.0 (SPSS, Inc., Chicago, IL, USA). Descriptive analyses were used to describe study variables. Independent t-tests and one-way analysis of variance (ANOVA) were performed to analyze the baseline equivalent between study groups. The generalized estimating equations were used to analyze the efficacy of the intervention for enhancing knowledge, knowledge, perceived benefits, perceived barriers, self-efficacy, and adherence to anticoagulant therapies in patients treated with oral anticoagulants for atrial fibrillation.

## Participant Flow Data Preparation Checklist

**Overview:** The Participant Flow module is a tabular summary of participants' progress through each stage of a study by assignment group. Use this checklist with the [Participant Flow Template](#) and [Results Data Element Definitions](#) to complete this module of the results section.

Select	Information to have available for Participant Flow	Data Element
	
 
Conceptual overview of the study design, including the type (e.g., single group, cross-over, parallel) and any distinct stages (e.g., double-blind then open-label)                             
 
Tip: Have a CONSORT flow diagram available.
 
 
 
	
	
 
Description of any significant study events that occurred after participants were enrolled, but before they were assigned to a study group (e.g., run-in phase or washout)
 
	[*]Pre-assignment Details
	
 
Number of groups that accurately describes the study design from participant assignment to completion                             
 
Tip: The number of groups is typically equal to the number of unique paths (participant experiences) in a CONSORT flow diagram, from beginning to end. Each group will be reported as a table column.
 
 
 
	*Arm/Group Information
	
 
For each group:                             
 
Title—Descriptive label for the group                                     
 
Tip: Use informative labels (e.g., "Placebo"), not generic labels (e.g., "Group 1"). The label will become the header for that table column.
 
 
 
Description—Detailed explanation of the interventions administered or the groups observed during each stage of the study                                     
 
Tip: Include details about the intervention (e.g., dosage, dosage form, frequency and duration of administration) or observation.
 
 
 
 
 
	*Arm/Group Title  *§Arm/Group Description
	
 
Number of discrete stages or intervals of activity in the study
 
	*Period(s)
	
 
Descriptive title for each period (the default for one Period is "Overall Study")                             
 
Tip: A Period Title should describe what happened during that period of the study. For example, "Double-blind (0 to 24 weeks)" and "Open-label (24 to 48 weeks)" are more descriptive than "Period 1" and "Period 2."
 
 
 
	*Period Title
	
 
Number of participants that Started and Completed each period:                             
 
Started—Participants initiating each period (e.g., the number of participants assigned or randomized to each group for that period)                                     
 
Tip: If the number of participants starting the first period is different from the total enrolled in the study, explain why in Pre-assignment Details.
 
 
 
Completed—Participants still in the study at the end of the period
 
Tip: If the unit of assignment is a unit other than participants, specify the name of the unit (e.g., eyes, lesions, implants) and provide the number of units.
 
Tip: Each unit of assignment (participants or units other than participants) should only be represented in one group. For example, if the unit of assignment is participants, do not count a participant more than once by including them in more than one group.
 
Tip: Use the Additional Milestone field to record any specific events or time points in the study between the Started and Completed milestones.
 
 
 
	*Started  *Completed  [*]Type of Units Assigned  Additional Milestone

*\*Required*

*\*§ Required if Primary Completion Date is on or after January 18, 2017*

*[\*] Conditionally required*

## Participant Flow Template

Recruitment Details	Patients with AFib were recruited from the cardiology clinics of two general hospitals in northern Taiwan. Potential participants were referred by cardiologists and screened by one of the investigators to determine their eligibility
[*] Pre-assignment Details	

Period ①		①		
*	Overall Study	EG	CG	
	*	Intervention Group	Control Group	
	*§ Arm/Group	Number of Participants ④	Number of Participants ④	Number of Participants
	* Started	36	36	
	[*] Milestone			
	[*] Milestone			
	[*] Milestone			
	* Completed	33	30	
	Not Completed	(automatically calculated)		
	Reason Not Completed Type ③			
	[*] Adverse Event			
	[*] Death			
	[*] Lack of Efficacy			
	[*] Lost to			
	[*] Physician			
	[*] Pregnancy			
	[*] Protocol			
	[*] Withdrawal by	1	2	
	[*] Other Change Medication	1	2	
	[*] Other Operation	1	0	

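### Change of medication and operation are counted as leaving the study, with no rule to follow or analyse those participants as randomised

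*Combined protocol and SAP*

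**What the plan says.** The purpose in the Study Protocol concerns adherence "in patients treated with oral anticoagulants for atrial fibrillation". It names no single drug and does not require that treatment stay unchanged.

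Under Methods, 36 participants are randomised to each arm and questionnaires are given at baseline, month 3 and month 6. On the setting: "The data collection took place at the waiting areas outside the outpatient clinics during the patients' visits to the clinics". Both arms also receive six follow-up telephone calls.

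The Participant Flow Template starts with 36 and 36 and gives "Completed 33 30" (intervention, then control). Its reasons for non-completion are "Withdrawal by" (1, 2), "Other Change Medication" (1, 2) and "Other Operation" (1, 0). The accompanying checklist explains the term: "Completed—Participants still in the study at the end of the period".

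The Outcome Measure Template describes the adherence population as those with a baseline and 24 weeks of follow-up, but enters 36 and 36 as the numbers analysed. It prints adherence of 8.1 (1.4) for intervention and 9.2 (2.2) for control, with no visit label. Data Analysis and the Statistical Analysis Template specify a GEE with group, time and their interaction. No section gives a rule for participants whose treatment changes, or for missing data.

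**The concern.** A medication change or an operation happens after randomisation and can plausibly be tied to how anticoagulants are taken, which is the outcome. If such an event ends follow-up, the month-6 comparison depends on what happened after assignment and is no longer purely between the randomised groups. It also moves away from the stated question: a participant switched from one oral anticoagulant to another is still treated with an oral anticoagulant for atrial fibrillation.

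The form records these four separately from withdrawals, so nothing shows that they declined further contact. The outcomes are questionnaires, and Methods already allows the investigator to read the items aloud. A trial of 72 has little room to lose informative scores, and the reader cannot tell from the form whether these four are in the reported result.

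**Working it through.** **1. Count check (Participant Flow Template).**
- Intervention: 36 - (1 + 1 + 1) = 33, which matches the 33 completed.
- Control: 36 - (2 + 2 + 0) = 32, against 30 completed. Two control losses have no listed reason. A row lost when the PDF was read cannot be excluded.
- Total loss: 3/36 (8.3%) versus 6/36 (16.7%), 9/72 = 12.5% overall; Fisher p = 0.48.
- Medication change or operation: 1 + 1 = 2 intervention and 2 + 0 = 2 control, so 4/72 = 5.6%, and 4 of the 9 non-completers.
- The extra control losses: 6 - 3 = 3, made up of one more withdrawal (2 versus 1) and the two unlisted losses. The events at issue contribute 2 - 2 = 0.

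**2. Who was analysed.** A population requiring 24 weeks of follow-up points to the 33 and 30 who completed. The entry of 36 and 36 points to everyone randomised. Both cannot describe one set of month-6 scores unless non-completers were scored at month 6, which no section says.

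**3. Sensitivity to the four scores.** Their scores are not in the documents, so this rests on assumptions: the printed values are month-6 completer means and SDs (n = 33 and 30), and the test is two-sided at 0.05. No alpha is stated as a design threshold. The method is a Welch t-test from summary statistics.

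Completers: difference 8.1 - 9.2 = -1.10; SE = √(1.4²/33 + 2.2²/30) = √(0.0594 + 0.1613) = 0.470; t = -2.34, p = 0.023.

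Adding two participants per arm, each at a shift k from the arm mean m: new mean M = m + 2k/(n + 2); new sum of squares = (n - 1)s² + n(m - M)² + 2(m + k - M)². With k of one SD (1.4 and 2.2), the means move by 2 × 1.4/35 = 0.080 and 2 × 2.2/32 = 0.1375. The SDs become 1.40 and 2.20, and the SE is 0.454.

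| Four added back (35 and 32) | Difference | p |
|---|---|---|
| At their arm means | -1.10 | 0.016 |
| Both arms 1 SD higher | -1.16 | 0.014 |
| Both arms 1 SD lower | -1.04 | 0.026 |
| Intervention higher, control lower (narrowing) | -0.88 | 0.058 |
| Intervention lower, control higher (widening) | -1.32 | 0.005 |

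The largest movement either way is 0.080 + 0.1375 = 0.22 points, about 20% of 1.10. A larger one-sided shift also crosses 0.05: only the intervention pair 4.4 points higher gives -0.85, p = 0.079.

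**The case against.** The strongest reply is that exclusion is not proved. The form enters 36 and 36 as analysed, and a GEE over three visits can use whatever data these participants gave before leaving. No section says when they left or whether they were scored at month 6. This stands. A reader might infer that the result describes only patients whose treatment was undisturbed, but the documents do not support that; they contradict themselves on the point. Earlier visits kept in the GEE would still not supply an observed month-6 score.

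A reader might also infer that these events produce the unequal loss of 3 versus 6. They do not: they are 2 versus 2. Nor can they be called expected in this population, because no rate is given beyond 4 of 72. Clinic-only collection is not shown to have caused any loss either. Equal counts do not, however, exclude bias, since the reasons and scores behind them may differ by arm.

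A third reply is that the questionnaires may not fit everyone. The form does not say what the medication was changed to. Someone who stopped anticoagulants has nothing for the adherence scale to refer to, and one of the listed instruments is specific to warfarin. This also stands, and it argues for recording that status and showing results both ways, not for ending follow-up.

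Finally, the flow table is a completed results form and Methods is written in the past tense, so collection may be over. That changes which remedy is available.

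**Conclusion.** The point holds in a limited form. As documented, two kinds of post-randomisation event count as leaving the study, the written analysis population would exclude those participants, and no rule says how they are handled. It concerns 4 of 72 participants, 2 per arm.

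Under the stated assumptions, three of the four 1-SD scenarios leave p below 0.05 and one does not. The four scores could therefore matter, but nothing shows that they reversed or created the result. The range depends on reading the unlabelled values as month-6 completer scores. If they already include all 72, there is nothing to add back, and the same Welch calculation with 36 and 36 gives -1.10, p = 0.014. That the form does not settle which reading applies is itself part of the problem.

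**What to change.** **If follow-up can still be changed:**
- State that a medication change or an operation does not end study follow-up. This concerns data collection only, not treatment.
- Give the month-3 and month-6 questionnaires to every randomised participant who has not withdrawn consent, by telephone when there is no clinic visit, and separately from the intervention content of the calls.
- Record the event, its date and the mode of collection.
- Replace the population requiring 24 weeks of follow-up with all randomised participants, in the GEE, using all available visits.
- Record who no longer takes an oral anticoagulant, and show the adherence result with and without them.

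**If data collection has ended:**
- Keep the available visits of these four in the GEE as randomised, and report whether month-6 scores exist.
- Add a sensitivity analysis over a range of assumed month-6 scores in both directions.
- Reconcile 36 and 36 analysed with 33 and 30 completed, label the visit of the printed means, and account for the two control losses without a listed reason.

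**Cost:** a few sentences of protocol text, a few extra questionnaires and one added analysis. Call timing is not given, so contacts at months 3 and 6 may need to be arranged. The downsides are mixed clinic and telephone modes, and possible influence of the treatment contact on self-reported adherence; separating the assessment from the call content reduces the latter but may not remove it.

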**Baseline Characteristics Template**

Age\* (use at least one)

ClinicalTrials.gov

* Arm/Group Title	EG	CG	Total	
* § Arm/Group Description ①	Intervention group	Control Group		
* Overall Number of Baseline Participants ②	36	36		③
[*] Baseline Analysis Population Description				
Age 20 years and over, diagnosis with AFib by a physician and receiving anticoagulation therapy				
Age, Categorical				
	<=18 years	0	0	③
	Between 18 and 65 years	13	13	③
	>=65 years	41	42	③
* Unit of Measure	Participants			
Age, Continuous				
* Measure Type	* Measure of Dispersion			
(Select One) Mean Median Least Squares Mean (LSM) Geometric Mean Geometric LSM	(Select One) Standard Deviation Inter-quartile Range Full Range			
	69.3	7.5	73.3	10
* Unit of Measure	years old			
Age, Customized				
* Measure Type	* Measure of Dispersion			
(Select One) Count of Participants ④ Mean Median Least Squares Mean (LSM) Geometric Mean Geometric LSM Number Count of Units ④	(Select One) Not Applicable ⑤ Standard Deviation Inter-Quartile Range Full Range			
[*] Row/Category Title ⑥		④ ⑤	④ ⑤	④ ⑤
[*] Row/Category Title ⑥		④ ⑤	④ ⑤	④ ⑤
[*] Row/Category Title ⑥		④ ⑤	④ ⑤	④ ⑤
* Unit of Measure				③
				④ ⑤

\* Required \*§ Required if Primary Completion Date is on or after January 18, 2017 [\*] Conditionally required

① Arm/Group Description describes details about the intervention strategy (e.g., dose, dosage form, frequency, duration) or groups evaluated.

② Overall Number of Units Analyzed and Type of Units Analyzed may also be specified.

③ Total values are automatically calculated for Overall Number of Baseline Participants and for data reported with a Measure Type of Number, Count of Participants, or Count of Units.

④ If Measure Type is a "count," percentage of participants/units is automatically calculated from Overall Number of Baseline Participants/Units Analyzed. The percentage can be hidden (display is optional).

⑤ Not Applicable should be used only if Measure Type is Number, Count of Participants, or Count of Units. No dispersion value is needed if Measure of Dispersion is Not Applicable.

⑥ [Optional] Add as many Rows/Categories as needed. If more than one is entered, a Row/Category Title and Baseline Measure Data are required for each row.

**Baseline Characteristics Template** *Sex/Gender\** (use at least one) **ClinicalTrials.gov**

* Arm/Group Title	EG	CG	Total
*§ Arm/Group Description ①	Intervention Group	Control Group	
* Overall Number of Baseline Participants ②	36	36	③
[*] Baseline Analysis Population Description			
Sex: Female, Male			
	Female	17	③
	Male	19	③
* Unit of Measure	Participants		

**Sex/Gender, Customized**

* Measure Type (Select One) Count of Participants ④ Mean Median Least Squares Mean (LSM) Geometric Mean Geometric LSM Number Count of Units ④	* Measure of Dispersion (Select One) Not Applicable ⑤ Standard Deviation Inter-Quartile Range Full Range	[*] Conditionally required				
[*] Row/Category Title ⑥		④ ⑤	④ ⑤	④ ⑤	③	④ ⑤
[*] Row/Category Title ⑥		④ ⑤	④ ⑤	④ ⑤	③	④ ⑤
[*] Row/Category Title ⑥		④ ⑤	④ ⑤	④ ⑤	③	④ ⑤
* Unit of Measure						

\* Required      \*§ Required if Primary Completion Date is on or after January 18, 2017

- ① Arm/Group Description describes details about the intervention strategy (e.g., dose, dosage form, frequency, duration) or groups evaluated.
- ② Overall Number of Units Analyzed and Type of Units Analyzed may also be specified.
- ③ Total values are automatically calculated for Overall Number of Baseline Participants and for data reported with a Measure Type of Number, Count of Participants, or Count of Units.
- ④ If Measure Type is a "count," percentage of participants/units is automatically calculated from Overall Number of Baseline Participants/Units Analyzed. The percentage can be hidden (display is optional).
- ⑤ Not Applicable should be used only if Measure Type is Number, Count of Participants, or Count of Units. No dispersion value is needed if Measure of Dispersion is Not Applicable.
- ⑥ [Optional] Add as many Rows/Categories as needed. If more than one is entered, a Row/Category Title and Baseline Measure Data are required for each row.

**Baseline Characteristics Template** Race\*, Ethnicity\*, and Region ClinicalTrials.gov

* Arm/Group Title	EG	CG	Total
*§ Arm/Group Description ①	Intervention Group	Control Group	
* Overall Number of Baseline Participants ②	36	36	72
[*] Baseline Analysis Population Description			
Race (NIH/OMB) ④			
American Indian or Alaska Native			
Asian	36	36	72
Native Hawaiian or Pacific Islander			
Black or African American			
White			
More than one race			
Unknown or Not Reported			
* Unit of Measure	Participants		
Ethnicity (NIH/OMB) ④			
Hispanic or Latino			
Not Hispanic or Latino			
Unknown or Not Reported			
* Unit of Measure	Participants		
Region of Enrollment			
United States			
Region/Country Name ⑤	Taiwan	36	
Region/Country Name ⑤			
Region/Country Name ⑤			
* Unit of Measure	Participants		

\* Required \*§ Required if Primary Completion Date is on or after January 18, 2017

[\*] Conditionally required

- ① Arm/Group Description describes details about the intervention strategy (e.g., dose, dosage form, frequency, duration) or groups evaluated.
- ② Overall Number of Units Analyzed and Type of Units Analyzed may also be specified.
- ③ Total values are automatically calculated for Overall Number of Baseline Participants and for each Baseline Measure.
- ④ If not using NIH/OMB categories, use Race/Ethnicity, Customized (not shown); if not collected, use Race and Ethnicity Not Collected (not shown).
- ⑤ [Optional] Region of Enrollment Baseline Measure is optional, but at least one Region/Country is required if reporting Region of Enrollment. Add as many Regions/Countries as needed.

**Baseline Characteristics Template**

**Study-Specific Measure\*§**

**ClinicalTrials.gov**

* Arm/Group Title	EG	CG	Total									
*§ Arm/Group Description ①	Intervention Group	Control Group										
* Overall Number of Baseline Participants ②	36	36		③								
[*] Baseline Analysis Population Description												
Patients with AFib currently receiving anticoagulation therapy												
[*] Study-Specific Baseline Measure Title												
History of anticoagulation therapy												
Baseline Measure Description												
* Measure Type (Select One) Count of Participants ④ Mean Median Least Squares Mean (LSM) Geometric Mean Geometric LSM Number Count of Units ④	* Measure of Dispersion (Select One) Not Applicable ⑤ Standard Deviation Inter-Quartile Range Full Range											
[*] Row/Category Title ⑥	Disease duration	65.6	45	④ ⑤	70.9	66.2	④ ⑤		④ ⑤	③		④ ⑤
[*] Row/Category Title ⑥				④ ⑤			④ ⑤		④ ⑤	③		④ ⑤
* Unit of Measure	month											

\* Required      \*§ Required if Primary Completion Date is on or after January 18, 2017      [\*] Conditionally required

① Arm/Group Description describes details about the intervention strategy (e.g., dose, dosage form, frequency, duration) or groups evaluated.

② Overall Number of Units Analyzed and Type of Units Analyzed may also be specified.

③ Total values are automatically calculated for Overall Number of Baseline Participants and for data reported with a Measure Type of Number, Count of Participants, or Count of Units.

④ If Measure Type is a “count,” percentage of participants/units is automatically calculated from Overall Number of Baseline Participants/Units Analyzed. The percentage can be hidden (display is optional).

⑤ Not Applicable should be used only if Measure Type is Number, Count of Participants, or Count of Units. No dispersion value is needed if Measure of Dispersion is Not Applicable.

⑥ [Optional] Add as many Rows/Categories as needed. If more than one is entered, a Row/Category Title and Baseline Measure Data are required for each row. Row/Category Titles are only required if more than one row.

## Outcome Measure Template

	Primary	Secondary	Other Pre-specified	Post-Hoc
* Outcome Measure	(Select One)			
* Outcome Measure	Anticoagulant medication adherence			
* Outcome Measure	Participants were monitor for up to 24 weeks, These is the score of participants who had been monitor for medication adherence. The study adapted Adherence to Refills Medications Scale (ARMS) assess the participants' medication adherence when taking anticoagulants			
Description	Ups to 24 weeks			
* Outcome Measure Time	Ups to 24 weeks			

More details available in the Results Data Element Definitions. April 2017

* Measure Type (Select One)	* Measure of (Select One)	EG		CG			
* Row/Category Title	* Row/Category Title						
* § Arm/Group Description		Intervention group		Control group			
* Number of Participants Analyzed	[*] Analysis: Population	36		36			
All participants with baseline and at least fellow up for 24 weeks							
Count of Participants ③	Not Applicable ④						
Mean	Standard deviation						
Median	Standard Error						
Least Squares Mean	Inter-Quartile Range						
[*] Row/Category Title	Medication adherence	8.1	1.4	9.2	2.2		③ ④
[*] Row/Category Title			③ ④		③ ④		③ ④
* Unit of	score						

*Statistical Analysis Template*

Statistical Analysis Overview	* Comparison Group Selection ①	 ✓ Arm/Group 1	 ✓ Arm/Group 2	 Arm/Group 3
	Comments ②			
	* Type of Statistical Test	(Select One) Superiority Non-inferiority Equivalence Other (for example, single group or other descriptive analysis)		
	[*] Comments ③			
Statistical Test of Hypothesis	[*] P-Value (if applicable)	0.05 [calculated value, not the a priori threshold for statistical significance]		
	Comments ②			
	[*] Method (required if p-value entered)	(Select One) ANCOVA ANOVA Chi-Squared Chi-Squared, Corrected Cochran-Mantel-Haenszel	Fisher Exact Kruskal-Wallis Log Rank Mantel-Haenszel McNemar	Mixed Models Analysis Regression, Cox Regression, Linear Regression, Logistic Sign Test t-Test, 1-Sided F-Test, 2-Sided Wilcoxon (Mann-Whitney) Other ( )
	Comments ②			
Method of Estimation	[*] Estimation Parameter (if applicable)	(Select One) Cox Proportional Hazard Hazard Ratio (HR) Hazard Ratio, Log	Mean Difference (Net) Median Difference (Final Values) Median Difference (Net) (generalized estimating equation) Odds Ratio (OR)	Odds Ratio, Log Risk Difference (RD) Risk Ratio (RR) Risk Ratio, Log
	Estimated Value	0.5 (calculated value)		
	Confidence Interval (if applicable)	Level: 95 % Confidence Interval	Number of Sides: (Select One) 2-sided	1-sided
	Parameter Dispersion	Lower Limit: _____	Upper Limit: _____	Type: (Select One) Standard Deviation Standard Error of the Mean
	Estimation Comments ②			
Other Statistical Analysis ④	A generalized estimating equation (GEE) 28 was used to model each outcome variable as a function of group effect, time effect, and group by time interaction effect.			

\* Required [\*] Conditionally required

- ① Use the checkboxes to select the Arms/Groups (pre-populated from the Outcome Measure) involved in the statistical analysis.
- ② (Optional) Include any relevant information about the row above (e.g., the null hypothesis, details of the power calculation, adjustment for multiple comparisons, the *a priori* threshold for statistical significance, the direction of the comparison). Do not include written results or conclusions.
- ③ If a non-inferiority or equivalence analysis, information on the definition of the non-inferiority or equivalence margin is required.
- ④ If the statistical analysis cannot be submitted using the Statistical Test of Hypothesis or Method of Estimation options, provide a description and the results

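### The adherence population line (baseline plus 24-week follow-up), the 36 and 36 analysed, and the 33 and 30 completers cannot all be right, and the documents do not show which is wrong

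*Combined protocol and SAP*

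**What the plan says.** The Methods paragraph of the Study Protocol says participants were "randomly assigned 1:1 to either the control group (n = 36) or the intervention group (n = 36) after completion of baseline questionnaires". On timing it says "Data were collected at baseline, third month, and sixth month in both groups". The analysis is by GEE; the Statistical Analysis Template gives the terms as group, time and their interaction.

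The Outcome Measure Template covers adherence, measured with an adapted refill-and-medication adherence scale over a time frame of up to 24 weeks. It enters 36 and 36 beside "Number of Participants Analyzed" and describes the population as "All participants with baseline and at least fellow up for 24 weeks". It gives one row of results, "Medication adherence 8.1 1.4 9.2 2.2", without naming the visit.

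The Participant Flow Template has one period, the overall study, with 36 started in each arm and "Completed 33 30". Among the reasons for not completing, it lists withdrawal (1 and 2), "Other Change Medication 1 2", and operation (1 and 0). The accompanying checklist defines the milestone as "Completed—Participants still in the study at the end of the period".

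Nothing in the documents says how missing scores are handled or how many participants were assessed at month 3 or month 6.

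**The concern.** The Outcome Measure Template is the only place that states an analysis population for adherence, the outcome named in the study's purpose. Its wording makes 24-week follow-up a condition of entry, yet the number beside it equals everyone randomised, although some participants in each arm did not complete.

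A reader therefore cannot tell whether the adherence result rests on all randomised participants or on those who remained to the end, nor how those who left were handled. If all 36 per arm were analysed, the description does not plainly fit and the treatment of missing scores is unstated. If the description was applied as written, the number is wrong and the comparison is no longer between the groups as randomised. The Completed row is a third entry that could be at fault.

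**Working it through.** **Inputs.** Started 36 and 36, completed 33 and 30, and the reasons for not completing (Participant Flow Template). Analysed 36 and 36, with the population line (Outcome Measure Template). Assessments at baseline, month 3 and month 6 (Study Protocol, Methods).

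**1. Can 36 and 36 be reproduced?**
- As all randomised: yes, it equals the number started in each arm.
- As baseline plus 24-week follow-up: no. If the study period ends at month 6, the number meeting the line is at most the number completed, 33 and 30, or 63 of 72.

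**2. Does the baseline half of the line explain the gap?** No. All 36 + 36 = 72 were randomised after completing baseline questionnaires. The instrument list in Methods does not name the adherence scale, so a baseline adherence score is presumed rather than stated. A missing baseline score could only lower the number qualifying.

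**3. Do the flow entries agree with themselves?**
- Intervention: 36 − 33 = 3 not completed; reasons 1 + 1 + 1 = 3. They agree.
- Control: 36 − 30 = 6 not completed; reasons 2 + 2 + 0 = 4. They do not agree. The listed reasons would fit 36 − 4 = 32 completers. Other reason cells are blank or may have been lost when the text was extracted.

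**4. Does the conflict depend on the doubtful control count?** No. Whether control completers number 30 or 32, they are fewer than 36. The intervention arm, whose entries agree, still has 33 against 36.

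**5. How many would the line remove if applied as plainly written?**
- With 30 control completers: 3 + 6 = 9 of 72, or 12.5%.
- With 32 control completers: 3 + 4 = 7 of 72, or 9.7%.

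**6. Is loss unequal between arms?** It is 3/36 (8.3%) against 6/36 (16.7%), two-sided Fisher exact p = 0.48; or 3/36 against 4/36 (11.1%), p = 1.0. Counts this small neither show nor rule out differential loss.

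**The case against.** The strongest reply is that 36 and 36 may simply be correct. GEE can use participants with partial follow-up, and the population line is garbled. If it was meant to require at least one follow-up, a participant seen at month 3 who later left would qualify. This stands as a possibility. It needs every non-completer to have given month-3 data, which the documents do not show, and the line would still need rewording before its number could be checked.

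A second reply is that the premise is assumed. The definition of Completed is generic form guidance, the study period has no stated end, and 24 weeks (24 × 7 = 168 days) falls slightly short of six calendar months. Someone might pass 24 weeks and still not complete. That is fair, but no assessment is scheduled between month 3 and month 6, so such a person would have no scheduled 24-week score.

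Third, the control Completed entry may itself be wrong. That is accepted: three entries are in question, not two.

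A reader might go further and infer that only completers were analysed, or that the adherence result is biased. The documents support neither. They do not say that anyone was excluded. The printed means do not identify their visit, and if they are model means, 36 and 36 is quite possible.

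**Conclusion.** The point holds as an inconsistency that leaves the adherence analysis set undefined. The population line, the number analysed and the Completed row cannot all be right on the plain reading, and the documents do not show which is wrong.

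This rests on two assumptions: that the line means what it appears to say about 24 weeks, and that the overall study period ends at month 6, taken as about 24 weeks. It does not rest on the uncertain control count, because the intervention arm is enough.

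At stake is whether 7 to 9 of the 72 randomised participants are in the comparison. Any effect on the adherence result is hypothetical. It should be fixed because the rule, applied as written, would set aside randomised participants, and because the correction is cheap. Confidence is moderate, given the garbled line and possible losses in the flow table.

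**What to change.** - Replace the population line with all randomised participants, analysed in the arm assigned, using every available baseline, month-3 and month-6 adherence score in the GEE already named.
- Make the number analysed match that definition, name the visit to which the printed means belong, and report N by arm and visit.
- State how missing adherence scores are handled. An analysis of 24-week completers should be a sensitivity analysis at most.
- Check the control Completed count and the reasons for not completing against source, and correct whichever entry is wrong.

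The cost is wording and verified table entries. A re-run on scores already collected is needed only if completers alone were analysed. No new participants or visits are required.
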